1.10 Timetable/Schedule of Events

Table 1. R21 Timeline		Year 1											
Month		1	2	3	4	5	6	7	8	9	10	11	12
Protocol manual writing and staff training													
Recruitment													
Intervention period													
Follow-up data collection													
Pilot study data analyses													
R33 protocol manual writing, institutional review board application and approval													
Recruit and hire R33 staff													

assessments will begin in month 6 and continue through month 9, and 16-week follow-ups will begin in month 8 and continue through month 11. In month 11, we will finalize our assessment of study feasibility. At the end of

The project timeline proposes to spend three months conducting start-up activities, with study recruitment beginning in month 4 and continuing through month 7. The intervention will begin in month 4 and continue through month 9, 8-week follow-up

month 11, we will prepare a report summarizing our feasibility findings for NCCIH and seek approval for continuing to a larger, fully powered, randomized controlled trial. Data collection for this pilot study will be 8 months.

2.0 Project Management

2.1 Research Staff and Qualifications

[name], the Principle Investigator on this project, is a clinical psychologist and faculty member at Rutgers-RWJ Department of Psychiatry. [name] has more than 15 years' of clinical and research experience with substance abusing and mentally ill populations. [name], Co-Investigator, has more than 25 years' experience conducting research in the area of mental health and addictions in New Jersey, including epidemiological studies, qualitative research and clinical trials.

All research staff will have a minimum of a Bachelor's degree or experience working with substance users. All investigators and key personnel will have undergone mandatory education in human research participant protection, including completing the Human Research Curriculum of Collaborative Institutional Training (CITI), "HIPAA Security" training, and "HIPAA Privacy" training. Research staff will participate in ongoing team meetings with the study investigators to discuss any issues that arise.

2.2 Resources Available

Facilities

Rutgers Robert Wood Johnson Medical School, Addiction Psychiatry Research Offices at [name]. The Division of Addiction Psychiatry is located in a clinical-research unit of 3000 sq. ft. which includes faculty and staff offices, sound proofing, and a conference room (where community advisory panel meeting will be held). In addition to several faculty members, Division office space is shared by administrative personnel, research assistants, and secretaries. Fax and copy machines are available in the Division offices.

New Brunswick Counseling Center (NBCC) at [name]. [name] has conducted several research studies at NBCC, and the clinic is extremely enthusiastic about being a research site for this project (see attached letter). The New Brunswick Counseling Center (NBCC) provides comprehensive, evidence-based, individualized, substance abuse treatment services. NBCC's staff includes a multidisciplinary team of medical, psychological, social work, and substance abuse professionals. NBCC currently approximately 500 patients receiving methadone maintenance treatment, and, in the past year, almost 90% of admissions to the center reported current cigarette smoking. The clinic is in central New Brunswick, NJ, within walking distance from where the Division of Addiction Psychiatry offices are located, making this location ideal for patient recruitment and collaboration. Office and group counseling space is available at the NBCC for the research staff to see study participants.

The Lennard Clinic. The Lennard Clinic, with two offices in Newark and Elizabeth, New Jersey ([name] and [name]), exists to enrich the quality of life of opioid dependent adults in Essex, Union and surrounding counties to reduce illicit drug use, decrease criminal activities, enhance health conditions and promote social/economic stabilities by providing superior treatment services. The Lennard Clinic provides: 1) medication Assisted Treatment (methadone, suboxone), 2) individual treatment, transition and discharge planning, 3) individual and group counseling, medical care for indigent clients, case management, and clinic based treatment on demand (CBTOD) free for eligible clients. The Newark site services approximately 700 clients on methadone maintenance treatment and the Elizabeth site serves approximately 300 clients on methadone maintenance treatment.

Medical Or Psychological Resources

Methadone clinic medical and psychological resources will be available to study participants. During assessment sessions, participants will be told that they do not need to discuss topics or disclose any information that makes them uncomfortable. The research assistant will be trained to deal with any distress related to the study interviews. Referrals for counseling or psychiatric evaluation will be made if necessary. If a participant expresses thoughts of harming himself or herself or others or discloses a child is at-risk, either verbally or on the study measures, a written protocol has been developed and confidentiality may be broken. A participant who endorses current thoughts of harming himself, herself, or others will be assessed by the methadone program clinical team to determine if the participant is safe to leave the clinic, if the individual is in the clinic or by [name], if contact with the participant was over the phone, to determine if further action needs to be taken to ensure the safety of the participant or others. [name] will be available to assess and address any medical adverse events that occur during the course of the study.

Research Staff Training

All research staff will have completed the online human subject's protection (CITI training). Staff will be trained and supervised by [name] and [name] on unbiased recruiting of study participants, data collection, and maintaining confidentiality. They will also be trained on assessing adverse events, tracking study participants, data entry, and procedures if a participant expresses intent to harm him/herself or others. A manual of procedures will be created for research staff and weekly research staff meetings will be held to assure protocol adherence and address any issues.

3.0 Multi-Site Research Communication & Coordination

N/A

4.0 Research Data Source/s

4.1 Primary Data-Subjects and Specimens

4.2 Subject Selection and Enrollment Considerations

A. Recruitment Details

Thirty participants will be recruited from the New Brunswick Counseling Center (NBCC) or the Lennard Clinic. Participants will be recruited from flyers providing study information posted in the methadone clinic. In addition, clinic staff will refer potential participants to the study and research assistants will recruit on-site at the clinic. The research assistant will approach clinic clients in the waiting area at different times and on different days of the week to ensure adequate sampling. The research assistant will introduce him/herself to individuals waiting in clinic waiting areas, tell them they are conducting a study of an intervention for people with chronic pain and in methadone treatment, and ask them if they are interested in hearing more about the study. Patients expressing initial interest in the research will be given more detailed study information by the RA and screened for study eligibility.

B. Source of Subjects

Participants will be recruited from the New Brunswick Counseling Center (NBCC) and the Lennard Clinic.

C. Method to Identify Potential Subjects

Research assistants will screen individuals for eligibility after identifying interested individuals receiving services at NBCC or the Lennard Clinic.

D. Subject Screening

▪ Inclusion Criteria

Subjects must be age 18 or older, English-speaking, been in methadone treatment for at least 3 months, and experience a non-malignant pain with an intensity level of 8 or higher on the Gracely Box Scale¹³ for a duration of 2 months or longer.

▪ Exclusion Criteria

Subjects will be excluded from participation if they do not meet the inclusion criteria above exhibit cognitive impairment (score <24 on the Mini Mental Status Exam¹⁹) or psychosis (positive SCID Psychotic Screen²⁰), are at suicidal risk (positive score on ASQ Suicide Risk Screening Tool²³), or unable to attend group sessions due to distance, work, commitments or other logistical problems, or are currently pregnant or breastfeeding or planning to be pregnant or breastfeeding the next 16 weeks.

E. Recruitment Materials

Flyers with study information and a phone number to reach research staff will be posted throughout the New Brunswick Counseling Center (NBCC) and the Lennard Clinic.

F. Lead Site Recruitment Methods

N/A

4.3 Subject Randomization

Since MORE is a closed group, we will randomize cohorts of 10-16 participants (depending on speed of recruitment) at each site to TAU or MORE with block randomization. Once we recruit at least 10 participants at a particular clinic, we will randomize participants to MORE or TAU, and the MORE group will begin. We estimate that we will recruit at least 10 participants per month.

4.4 Secondary Subjects

N/A

4.5 Number of Subjects

A. Total Number of Subjects

Total number of subjects to be accrued is 31.

B. Total Number of Subjects If Multicenter Study

N/A

C. Require Number of Subjects to Complete Research

N/A

D. Feasibility of Recruiting

Subjects will be recruited for up to four months. NBCC serves approximately 500 MMT clients and the Lennard Clinic serves approximately 1000 MMT clients at two sites.. Based on the prior research studies

conducted at these clinics and the high amount of clients served, there are no anticipated problems in recruiting ample subjects.

4.6 Consent Procedures

A. Consent

- **Documenting Consent**

If you will document consent in writing, provide a list of each document here and upload your consent document(s) in eIRB. For guidance see HRP-091.

Consent for Study Participation

- **Waiver of Documentation Of Consent**

N/A

- **Waiver or Alteration of Consent Process**

- (i) **Waiver or Alteration Details**

N/A

- (ii) **Destruction of Identifiers**

N/A

- (iii) **Use of Deception/Concealment**

N/A

B. Consent Process

- **Location of Consent Process**

The informed consent process will take place at NBCC or the Lennard Clinic, in a private room reserved for the research study to take place.

- **Ongoing Consent**

N/A

- **Individual Roles for Researchers Involved in Consent**

The role of the individuals listed in the application as being involved in the consent process.

Study recruiters/research assistants, who have been trained in the study protocol and the process for obtaining consent, will consent subjects for the study.

- **Coercion or Undue Influence**

Those who choose to participate will complete a written, informed consent process before any study procedures are performed. A signed copy of the informed consent will be given to the study participants. Research staff will read the consent form out loud to any individuals who are unable to read the consent form on their own. Topics covered in the consent form will include a description of study procedures, the time involved, the right to withdraw at any time without penalty, procedures used to protect participant anonymity, information on the use of data, the potential benefits and risks of participating in the study, and limits of confidentiality regarding expressions of suicidal ideation, homicidal ideation, or a child at risk. Research staff will be trained to note signs that suggest that the individual is unable to consent and will: 1) ask permission from the individual before questioning him/her; 2) observe for signs of illness, intoxication, and other reasons causing individuals to be unable to consent; 3) assess orientation to person, place, time, and situation; and, 4) ask the potential participant to paraphrase the study requirements.

4.7 Special Consent/Populations

A. Minors-Subjects Who Are Not yet Adults

- **Criteria for Consent of Minors**

N/A

- **Wards of the State**

1. Research in NJ Involving Minors

N/A

2. Research Outside of NJ Involving Minors

N/A

■ **Parental Permission**

N/A

■ **Non-Parental Permission**

N/A

■ **Assent Process**

N/A

■ **Non-English Speaking Subjects**

N/A

B. Adults Unable to Consent / Cognitively Impaired Adults (for *interventional studies*)

N/A

4.8 Economic Burden and/or Compensation for Subjects

A. Expenses

Subjects will not incur any costs other than their time for participating in the study.

B. Compensation/Incentives

Participants will receive a \$30 gift card for completing the baseline assessments and drug screen, \$40 for the 8-week assessments and drug screen, and \$50 for the 16-week visit. At each of the baseline and 8-week visits, participants will also receive a \$20 gift card for completing the cognitive assessments. Also, participants will receive approximately 25¢ for completing each of two daily EMA assessments (e.g., \$20 for 25%, \$30 for 50%, \$40 for completing 75%, and \$50 for completing 100% of EMA assessments). In sum, participants who complete all study assessments will receive \$210 total as well as a smartphone. Payments will be made in the form of a gift card. Participants randomized to the intervention condition will receive a \$5 gift card for attending each intervention session (up to \$40 total). These amounts are deemed fair compensation for the amount of time participants are asked to spend, without being large enough to be considered coercive.

C. Compensation Documentation

All participant incentive payments will be fully documented on incentive logs, which will record the date, amount, subject ID number, and name of the research staff distributing the payment for each incentive paid. Participants will also be asked to initial the log entry indicating that they have received their payment.

4.9 Risks to Subjects

A. Description of Subject Risk

This study involves accepted forms of treatment and assessment. Risks to subjects are minimal. The main risk associated with the study is discomfort related to talking about personal issues in study assessments and group sessions. However, participants do not have to talk about anything they do not want to. Loss of confidentiality is a risk. However, group participants will be informed about the importance of confidentiality and study staff will be trained to protect participant confidentiality. While we are not actively recruiting participants with an existing psychological disorder, it is possible we enroll individuals who we subsequently find to be suicidal or have other mental health problems. Personal information may be disclosed to a participant's clinic counselor, program director, or other public safety of healthcare personnel if study staff believes, based upon information reported during intervention sessions or

through research assessments, that a participant may harm himself or herself or others. Protocols have been developed to manage unexpected emergencies involving individuals with mental health problems, as well as to manage risks associated with participant discomfort and loss of confidentiality. If the study staff determine that the participant is a harm to him/herself or others to the extent that, based on the implementation of the protocol, it is a new or worsening symptom, it will be considered an adverse event. If the research staff determines that loss of confidentiality is required to protect the individual or others, the event will be reported to the IRB and NIH as a serious adverse event.

B. Procedures for Risks to Embryo, Fetus, and/or Pregnant Subjects

N/A

C. Risks to Non-Subjects

N/A

D. Assessment of Social Behavior Considerations

▪ Reasonably Foreseeable Risks

A risk associated with this study, among people who have substance use disorder and possibly a mental health disorder, is discomfort related to talking about personal or sensitive issues in study assessments and group sessions. However, participants do not have to talk about anything they do not want to. Loss of confidentiality, in general or about sensitive information like substance use, is a risk. While we are not actively recruiting participants with an existing psychological disorder, it is possible we enroll individuals who we subsequently find to be suicidal or have other mental health problems. Personal information may be disclosed to a participant's clinic counselor, program director, or other public safety of healthcare personnel if study staff believes, based upon information reported during intervention sessions or through research assessments, that a participant may harm himself or herself or others. Protocols have been developed to manage unexpected emergencies involving individuals with mental health problems, as well as to manage risks associated with participant discomfort.

▪ Risk Of Imposing An Intervention On Subject With Existing Condition.

All interventions will be voluntary and participants can discontinue at any time.

▪ Other Foreseeable Risks

N/A

▪ Observation And Sensitive Information

N/A

E. Minimizing Risks

During assessment sessions, participants will be told that they do not need to discuss topics or disclose any information that makes them uncomfortable. The study clinicians and research assistant will be trained to deal with any distress related to the study assessments or group sessions. Referrals for additional counseling or psychiatric evaluation will be made if necessary. If a client expresses thoughts of harming himself or herself or others either verbally or on the study measures, a written protocol has been developed and confidentiality may be broken. Participants will be made aware during the consent process that confidentiality may be broken if the study staff determine that he or she may be a risk to him or herself or others. As noted previously, assessments will occur in the methadone clinic where clinical staff will be present to assist in managing unexpected mental health emergencies. A participant who endorses current thoughts of harming himself, herself, or others will be assessed by study clinical staff and, if necessary, the participant's substance abuse counselor and/or the clinical director of the clinic to determine if the participant is safe to go home or if further action needs to be taken to ensure the safety of the participant or others. If a participant discloses information about harming him or herself or others

during a telephone interaction, [name] will be available to assess the participant and determine appropriate course of action. Written protocols have been established for these circumstances.

Group participants will be informed about the importance of confidentiality and study staff will be trained to protect participant confidentiality. Data will be collected in private areas to prevent disclosure of information. Also, to assure confidentiality, data and recordings will be secured in a database management system, password protected files, and in secure file cabinets. Data collection forms, databases and recording will not include identifiers other than a study ID code. The key to the code will be kept separately in a locked file. Informed consent forms will be kept separated in a locked file in the same office. Three levels of security are provided to prevent unauthorized persons from accessing data: password protection, computer or file cabinet locks, and a locked office. In addition, we will obtain a Certificate of Confidentiality from the National Institutes of Health that protects study data from forced disclosure.

F. Certificate of Confidentiality

Since all NIH studies are automatically issued a Certificate of Confidentiality (COC), the study is already covered by a COC. As of October 1, 2017, NIH funded researchers will no longer have to request a CoC, nor will they receive an actual certificate. The CoC will be issued automatically to NIH funded grants, cooperative agreements, contracts and intramural research projects research funded wholly or in part by the NIH that collects or uses identifiable, sensitive information.

G. Potential Benefits to Subjects

Participants in the MORE study group will receive the benefit of free group therapy sessions. Further, participants who do not use opioids or are better able to manage their chronic pain as a result of this study will gain important health and quality of life benefits. Because the risk of receiving free group treatment is very small, and the potential benefits for individual participants and society are quite large, the risk/benefit ratio is clearly weighted on the side of the benefit for those randomized to the intervention condition. Further, if MORE is ultimately found to be effective, in the future, it could help improve quality of life and prevent relapse for all individuals with chronic pain and in methadone treatment, including all of the participants. However, this study could also have no direct benefit to study participants.

H. Provisions to Protect the Privacy Interests of Subjects

Group participants will be informed about the importance of confidentiality and study staff will be trained to protect participant confidentiality. Data will be collected in private areas to prevent disclosure of information. Also, to assure confidentiality, data and recordings will be secured in a database management system, password protected files, and in secure file cabinets. Data collection forms, databases and recording will not include identifiers other than a study ID code. The key to the code will be kept separately in a locked file. Informed consent forms will be kept separated in a locked file in the same office. Three levels of security are provided to prevent unauthorized persons from accessing data: password protection, computer or file cabinet locks, and a locked office. Transmission of EMA data will be encrypted and data will not be stored on participants' mobile phones. The REDCap system, a HIPPA compliant, secure system will be utilized to collect and manage all EMA data and EMA data will not contain any identifying information. In addition, we will obtain a Certificate of Confidentiality (COC) from the National Institutes of Health (NIH) that protects study data from forced disclosure. NIH automatically issues a COC for all NIH funded research.

I. Research Team Access to Subject Data

Drs. [name] and [name] and the research staff will have access to all data stored on password protected files in Rutgers offices. All study data will be anonymous, and will contain no personal identifiers.

4.10 Secondary Data – Records/Chart Reviews/Databases/Tissue Banks/etc.

N/A

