6.3 Data and Safety Monitoring

A. Periodic Data Evaluation

Describe the plan to periodically evaluate the data collected regarding both harms and benefits to determine whether subjects remain safe. The plan might include establishing a data monitoring committee and a plan for reporting data monitoring committee findings to the IRB and the sponsor.

The Data and Safety Monitoring Board (DSMB) will meet every 3 months to monitor and evaluate the safety of participants throughout the course of the research study. The DSMB will:

- Assess the performance of the study with respect to participant recruitment, retention and follow-up, protocol adherence, and data quality and completeness.
- Monitor interim data regarding the safety of the study regimes.
- Review and consider any protocol modifications or ancillary studies proposed by study investigators after the main trial begins to ensure that these do not negatively impact on the main trial.
- Advise the Institutional Review Board as to whether the protocol should continue as scheduled or undergo a modification due to a finding from the monitoring process.

B. Type of Data Evaluated

Include what data are reviewed, including safety data, untoward events, and efficacy data.

The study investigators and the DSMB will be responsible for data safety and monitoring. Quarterly, the DSMB and the investigators will monitor the cumulative safety data during the period when participants are in the study. They will: 1) assess the performance of the study with respect to participant recruitment, retention and follow-up, protocol adherence, and data quality and completeness, to help ensure the likelihood of successful and timely trial completion; 2) monitor interim data regarding the safety of the study regimens; 3) review and consider any protocol modifications by the study investigators after the trial begins to ensure that these do not negatively impact on the study; and 4) advise the Institutional Review Board and NIH as to whether the protocol should continue as scheduled or undergo a modification due to a finding from the monitoring process.

C. Collection of Safety Information

Explain how the safety information will be collected (e.g., with case report forms, at study visits, by telephone calls with participants).

Safety information will be collected during participant's assessments, telephone calls with participants, conversations with clinic staff, and MORE group sessions.

D. Frequency of Data Collection

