The frequency of data collection, including when safety data collection starts.

Safety data collection will begin with collection of the first baseline assessment and continue through the end of the follow-up data collection period (12 months total). In addition to using assessment data to monitor safety, study clinicians will record any adverse events that they become aware of during MORE group sessions and study Investigators will ask NBCC and the Lennard Clinic personnel, with participant consent, to notify the research team should they become aware that any study participant has been hospitalized or experienced any other adverse event. Such notifications will be requested throughout the study period. All adverse events will be recorded on spreadsheets and will include details of the adverse event and whether or not it was study-related. Numbers and types of events and other quantifiable event details will be entered into a database for analysis.

E. Reviewer of Data

Who will review the data?

The DSMB will meet on a quarterly basis to monitor the cumulative safety data during the period when participants are in the study. The DSMB will monitor the study according to the guidelines specified in the study protocol and the operating procedures established at the initial DSMB meeting, unless the DSMB determines during the course of the trial that modification of the guidelines is in the best interest of the study and its participants. Such a decision may be based on new information that emerges during the course of the study (e.g., publication of the results of a similar study), realization of inappropriate initial study assumptions, or the occurrence of an unanticipated scenario.

F. Schedule of Review of Cumulative Data

The frequency or periodicity of review of cumulative data.

Under supervision of the investigators, the Research Assistant will conduct monthly descriptive summaries on all data to ensure their accuracy. This will not involve completing any statistical comparisons. If problems are noted in data entry (e.g., out of range values, missing values), the Research Assistant and the investigators will investigate the root cause, and solutions to rectify the problem.

G. Tests for Safety Data

The statistical tests for analyzing the safety data to determine whether harm is occurring.

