Basic statistical tests, including frequency distributions, Anovas and t-tests, will be carried out to compare the control and intervention groups on numbers and types of adverse events within specific time frames in order to insure the safety of the intervention.

H. Suspension of Research

Any conditions that trigger an immediate suspension of the research.

Considering the minimal risk nature of the intervention, we do not anticipate any serious adverse events that could trigger the immediate suspension of the research.

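### The only stated criterion for a serious adverse event is a break of confidentiality; hospitalisation has no stated seriousness class and no individual reporting route or timing

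*Combined protocol and SAP*

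**What the plan says.** Section 4.9 A gives two rules in consecutive sentences. The first covers a participant judged a danger to self or others: to the extent that "it is a new or worsening symptom, it will be considered an adverse event". The second says that if staff decide that a break in "confidentiality is required to protect the individual or others, the event will be reported to the IRB and NIH as a serious adverse event".

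Section 2.2 (Medical or Psychological Resources) adds another ground for disclosure besides thoughts of harm. If a participant "discloses a child is at-risk, either verbally or on the study measures, a written protocol has been developed and confidentiality may be broken".

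Section 6.3 D deals with events learned from the clinics. With participant consent, clinic personnel are asked to tell the research team if they become aware that "any study participant has been hospitalized or experienced any other adverse event". On what is kept: "All adverse events will be recorded on spreadsheets and will include details of the adverse event and whether or not it was study-related".

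Section 6.3 B states that, quarterly, "the DSMB and the investigators will monitor the cumulative safety data". Section 6.3 G compares the arms on numbers and types of adverse events. Section 6.3 H uses the term serious adverse event once, without defining it: "we do not anticipate any serious adverse events that could trigger the immediate suspension of the research".

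**The concern.** Seriousness is normally meant to tell an oversight body how badly a participant fared. Here the one stated rule depends on whether staff had to tell someone outside the study. A call to a clinic counsellor can therefore generate a serious-event report to the IRB and NIH, while a hospital admission that needed no such call meets no stated criterion. The admission is still recorded as an adverse event, but no section says whether it is serious, who receives an individual report, or when.

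Two things are at stake. First, a reader of the serious-event reports could not take them as a record of clinical harm. Second, the stated sources of information that can lead to disclosure are not equal between arms, so a disclosure-driven count has more opportunity to rise in MORE for reasons unrelated to harm. This matters in a population for which section 1.2 itself names opioid overdose as a possible consequence of pain.

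**Working it through.** The plan states no figure on this point, so there is nothing to reproduce. The check sets the rules side by side and applies them to concrete cases.

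**Inputs.** The adverse event rule and the serious adverse event rule (4.9 A); the child-at-risk ground for breaking confidentiality (2.2); notification and logging of hospitalisation (6.3 D); quarterly review (6.3 A, B and E); the arm comparison (6.3 G); the undefined use of the term (6.3 H).

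**Two readings of the serious-event sentence.** *Literal*: any situation in which confidentiality must be broken to protect someone is reported as serious. *Nested*: the event in the second sentence is the adverse event of the sentence before, so it must also be new or worsening.

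| Case | Adverse event? | Serious, literal reading | Serious, nested reading |
|---|---|---|---|
| New suicidal ideation, counsellor informed | Yes (4.9 A) | Yes | Yes |
| Unchanged ideation not detected at screening, counsellor informed | No (4.9 A) | Yes | No |
| Child at risk, confidentiality broken, no participant symptom | Not under 4.9 A | Yes | No |
| Hospital admission, for example for overdose, no break of confidentiality | Yes (6.3 D) | No | No |

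**What follows.**

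1. The last row gives the same answer under both readings. A hospitalisation without a break of confidentiality meets no stated serious-event criterion. This part does not depend on interpretation.
2. The second and third rows change with the reading. Whether serious events are a subset of adverse events is therefore ambiguous, not settled.
3. On reporting, section 6.3 D gives a route into the research team (clinic notification) and a record (details and relatedness). Sections 6.3 A and B give a route for cumulative data to the DSMB and for DSMB advice to the IRB and NIH. No section gives a route or timing for an individual report of a hospitalisation. The only individual report to the IRB and NIH as a serious event is the one in 4.9 A.

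**Opportunity for disclosure by arm.** Section 4.9 A names two sources of information that can lead to disclosure: intervention sessions and research assessments. Both arms have three interviews of up to 90 minutes, so 3 × 1.5 = 4.5 hours at most, plus the same cognitive testing and smartphone prompts. Only MORE has the group sessions: 8 × 2 = 16 hours if all are attended. These hours show unequal opportunity. They are not an estimate of how many more disclosures would occur, and the protocol gives no rate from which to make one.

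**The case against.** The strongest reply has four parts.

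*The two sentences belong together.* The event called serious is naturally the adverse event just described. Section 4.2 D also excludes anyone with a positive suicide-risk screen, so ideation found after enrolment would usually be new or worsening. And section 2.2 says that confidentiality may be broken for a child at risk without calling that a serious adverse event. This stands in part. A reader might infer that the plan definitely lets an event be serious without being adverse; the text supports only an ambiguity, and the unchanged-ideation case is likely to be uncommon.

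*Hospitalisations are not held back.* A reader might infer that a hospitalised event waits for the next quarterly DSMB meeting. The documents do not say so. Clinics are asked to notify throughout the study, investigators share responsibility for safety monitoring, and section 2.2 makes a designated person available to address medical adverse events. What can be said is that the timing of individual reporting is not stated. Likewise, section 6.3 D does not exclude a seriousness entry on the log; it simply mentions none.

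*The trial's conclusions do not rest on serious-event counts.* This stands. They are not an endpoint (sections 1.3 and 1.6 B), and progression to the larger trial depends on recruitment, retention and follow-up (section 1.1 B). The arm comparison in 6.3 G uses all adverse events, so hospitalisations are counted there. The documents do not support a claim that the decision on the larger trial would rest on miscounted events.

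*Other documents may define seriousness.* The protocol refers to a manual of procedures, written emergency protocols and DSMB operating procedures, none of which was available. This limits the finding to the text reviewed. It does not remove the need to align section 4.9 A with whatever those documents say.

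None of the four supplies a stated seriousness class or an individual reporting route for a hospitalisation.

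**Conclusion.** The point holds in this form: the one stated criterion for a serious adverse event is a break of confidentiality, and hospitalisation, although captured and subject to quarterly cumulative review, has no stated seriousness classification and no stated individual reporting route or timing. Section 4.9 A is a rule that, if followed, sorts events by disclosure instead of outcome, so this is more than a missing definition. Whether serious events must also be adverse events is unclear and should be settled in the text.

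The consequence is confined to safety reporting to the IRB and NIH and to how serious events compare between arms. It does not touch the feasibility milestones or the exploratory efficacy outcomes. No numerical size is claimed, since the effect depends on how many disclosures and hospitalisations occur in 31 participants. The conclusion assumes that no document outside the reviewed text already defines seriousness by outcome. The change should be made, and it is inexpensive.

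**What to change.** Reconcile sections 4.9 A and 6.3 A, B, D and H as follows.

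- Record a break of confidentiality as its own reportable event, with its own count by arm, separate from adverse events.
- Add a seriousness field to the adverse event log, and classify every logged event, including those notified by the clinics, as serious or not by its outcome. The list of outcomes should be written out and should include hospitalisation.
- State that serious adverse events are a subset of adverse events.
- State one route and one timing for reporting serious events individually to the IRB and NIH, distinct from the quarterly cumulative review.
- Use the same definition wherever the term appears, including section 6.3 H.

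If the manual of procedures or the DSMB operating procedures already define seriousness, a cross-reference and an edit to section 4.9 A are enough.

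The cost is protocol wording and one log column. The downside is a few more individual reports.
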